2. STUDY OBJECTIVES

The objectives of this study are:

Primary objective:

1. To describe in routine clinical practice the effectiveness of the interferon-free ABBVIE REGIMEN ± RBV in patients with CHC as evidenced by sustained virological response at 12 weeks after end of treatment (SVR12)

Secondary objectives:

2. To provide real world evidence for predictive factors of virological response
3. To describe the pattern of real world use of the ABBVIE REGIMEN ± RBV with respect to different patient and treatment characteristics
4. To evaluate the influence of adherence on treatment outcome in routine clinical practice
5. To collect information on co-morbidities and concomitant medication in the Belgian population
6. To describe the tolerability of the ABBVIE REGIMEN ± RBV
7. To determine the impact of the ABBVIE REGIMEN ± RBV on healthcare resource utilization
8. To evaluate the contribution of the patient support program (PSP) to disease control, treatment continuation over time, patient satisfaction and PSP utilization
9. To assess viral resistance patterns

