4.2 Statistical and Analytical Methods

4.2.1 Analysis Populations and Analysis Groups

Population of Patients Enrolled [EP]

The population of patients enrolled comprises all patients who voluntarily sign and date an informed consent prior to inclusion into the study and data were captured in the eCRF.

Target Population [TP]

Patients will be included if the following applies:

- Age at least 18 years
- Confirmed CHC with genotype 1 and/or 4 only, receiving combination therapy with the interferon-free ABBVIE REGIMEN \pm RBV. The prescribed ABBVIE REGIMEN needs to be known.
- Have voluntarily signed and dated an informed consent prior to inclusion into the study
- Must not be participating or intending to participate in a concurrent interventional therapeutic trial

Core Population [CP]

The core population is defined as all patients of the target population (TP) (definition see above), who are adequately treated according to the standard of care and within local label recommendations for their specific disease characteristics (cirrhotic status, genotype). The following patients will be excluded from the CP:

- Patients with unknown fibrosis status
- Cirrhotic patients with genotype 1a not receiving ribavirin
- Patients with genotype 1 for whom 2DAA instead of 3DAA is prescribed
- Patients with genotype 4 not receiving RBV

Non-Core Population [NCP]

Patients in the TP who are not in the CP.

Core Population with Sufficient Follow-up [CPSFU {12, 24}]

In addition, the core population with sufficient follow-up data regarding SVR12 or SVR24, respectively, is defined as all CP patients,

- who have evaluable HCV RNA data ≥ 70 days or >126 days, respectively, after the last actual dose of the ABBVIE REGIMEN
- or a HCV RNA value ≥ 50 IU/mL at the last measurement
- or had HCV RNA <50 IU/mL at the last measurement, but no HCV RNA measurement ≥ 70 days or >126 days, respectively, after the last actual dose of the ABBVIE REGIMEN due to reasons related to safety (e.g. dropped out due to adverse event) or virologic failure (e.g. virologic failure such as relapse is reported in the electronic case report form (eCRF) but date and value of the corresponding HCV RNA test is missing).

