This means only patients who had virological response at their last on-treatment or post-treatment measurement, but had no HCV RNA measurements ≥ 70 days or >126 days, respectively, post-treatment for reasons not related to safety or effectiveness (e.g. lost-to-follow-up or patient not willing to perform an additional HCV RNA test ≥ 70 days or >126 days, respectively, post-treatment) will be excluded from this analysis.

Safety population [SP]

The safety population is defined as all enrolled patients who received at least one dose of the ABBVIE REGIMEN. The prescribed ABBVIE REGIMEN needs to be known.

EP and TP analysis groups

The EP/TP analysis groups are defined according to the patient's fibrosis status and genotype/subtype and standard summaries are structured as follows:

- Total (regardless of cirrhosis status)
 - (1) Total (regardless of genotype)
 - (2) G1 (Total)
 - (3) G1a (including mixed G1 subtypes and patients with G1 unknown subtype)
 - (4) G1b
 - (5) G4 (non-G1)
 - (6) Other/unknown genotype (*only for EP*)
- Patients with cirrhosis
 - (7) Total (regardless of genotype)
 - (8) G1 (Total)
 - (9) G1a (including mixed G1 subtypes and patients with unknown G1 subtype)
 - (10) G1b
 - (11) G4 (non-G1)
 - (12) Other/unknown genotype (*only for EP*)
- Patients without cirrhosis
 - (13) Total (regardless of genotype)
 - (14) G1 (Total)
 - (15) G1a (including mixed G1 subtypes and patients with unknown G1 subtype)
 - (16) G1b
 - (17) G4 (non-G1)
 - (18) Other/unknown genotype (*only for EP*)
- Patients with unknown fibrosis status
 - (19) Total (regardless of genotype)
 - (20) G1 (Total)
 - (21) G1a (including mixed subtypes and patients with unknown subtype)
 - (22) G1b
 - (23) G4 (non-G1)
 - (24) Other/unknown genotype (*only for EP*)

(HCV genotypes will be combined as follows: G1 [total], G1a*, G1b, G4 [non-G1]. * includes mixed or other G1 subtypes and patients with unknown G1 subtypes.

Most recent stage of liver fibrosis will be categorized as follows: No cirrhosis/Transition to cirrhosis, Cirrhosis. Only one method should be selected by the physicians to report stage of fibrosis. Nevertheless, if there are multiple answers the following priority will be used:

1. Biopsy,
2. Non-invasive,
3. Clinical/best guess.

For biopsy as assessment method the respective categories are defined as follows:

- “No cirrhosis” is defined by “No fibrosis”, “Mild/minimal fibrosis”, “Moderate fibrosis”

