4.2.3 Handling of missing data

No data will be imputed for any effectiveness or safety analyses except for the analyses of the HCV RNA endpoints and certain PRO endpoints. The discussion of missing data imputation for the PRO endpoints is included in section 4.2.7.2.3.

HCV RNA values will be selected for an RVR, EOTR and SVR analysis based on visit windows as defined in Table 3. When there is no HCV RNA value in a visit window based on defined visit windows, the closest values before and after the window, regardless of the value chosen for the subsequent and preceding window, will be used for the flanking imputation described below. For analysis of RVR, EOT and SVR, if a subject has a missing HCV RNA value at a post-Day 1 visit but with undetectable or unquantifiable (\leq 50 IU/mL) HCV RNA levels at both the preceding value and succeeding value, the HCV RNA level will be considered undetectable or unquantifiable, respectively, at this visit for this subject. In addition, if a subject has an unquantifiable HCV RNA level at the preceding value and an undetectable HCV RNA level at the succeeding value, or vice versa, the HCV RNA level will be imputed as unquantifiable at this visit for this subject.

For analyses of RVR, subjects still missing a value for the visit after flanking imputation will be imputed as a failure. For EoTR and SVR analysis, if there is no value in the appropriate window after flanking imputation but there is an HCV RNA value after the window, then it will be imputed into the EoTR or SVR window respectively. Subsequent to this flanking imputation, if a subject is missing a value for the visit window associated with the analysis, the subject will be imputed as a visit failure (i.e., not undetectable or unquantifiable).

If a subject starts another treatment for HCV, then all HCV RNA values for this subject measured on or after the start date of the new HCV treatment will be excluded from analyses. The subject will be considered a failure for summaries of viral response at all time points after the start of the new HCV treatment.

Due to the non-interventional nature of this study several different methods for determination of the HCV RNA value can be applied. For the purpose of the statistical analysis, a HCV RNA measurement is considered ≤ 50 IU/mL,

- if a PCR test was used

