4.2.7 Analyses of the Objectives

4.2.7.1 Primary Effectiveness Variable

The primary objective of this study is to estimate the SVR12 rates in HCV patients treated according to the ABBVIE Regimen.

Therefore the simple percentage of patients achieving SVR12 (for definition see section 4.1.1) will be calculated and a two-sided 95% confidence interval (CI) of the percentage will be computed based on the Wilson's Score method.

The primary effectiveness analysis on clinical outcomes will be performed on all patients in the CP stratified by genotype and cirrhosis status and overall.

In the framework of sensitivity analyses the primary analyses will be repeated for the CPSFU. Furthermore, the SVR12 rates will be also determined for all patients of the NCP.

An overview of Tables is given in Table 8.

The layouts of the tables mentioned above are provided in Part II of the SAP (Table Shells).

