4.2.7.2 Secondary Variables

4.2.7.2.1 Secondary Effectiveness Variables

Response

For the other response rates (i.e. SVR24, EoT response rate, relapse rate), the simple percentage of patients and a two-sided 95% confidence interval (CI) of the percentage will be computed (based on the Wilson's score method) as well. The EoT response rate will be reported for CP and the SVR24 rate will be reported for the respective CPSFU, stratified by genotype and cirrhosis status and overall. The relapse rates will be estimated stratified by SVR window (i.e. during SVR12 window=relapse₁₂, during SVR24 window=relapse₂₄) and stratified by genotype

and cirrhosis status and overall in patients of the CP with EoT response who fulfilled the following criteria:

- completed treatment as defined previously,
- had at least one HCV RNA measurement ≥ 70 days post-treatment or was a treatment failure between EoT and 70 days post-treatment.

Viral breakthrough rates [defined as at least one documented HCV RNA <50 IU/mL followed by HCV RNA ≥ 50 IU/mL during treatment] will be estimated overall and stratified by genotype and cirrhosis status in all patients of the CP, who have at least one undetectable or unquantifiable, on-treatment HCV RNA measurement and at least one on-treatment or EoT measurement thereafter.

Non-Response

In another table, the numbers and the percentages of the SVR12 non-responder categories and responder will be summarized for CP patients, overall and stratified by genotype and cirrhosis status. The following SVR12 non-response categories will be considered:

- On-treatment virologic failure (breakthrough [defined as at least one documented HCV RNA <50 IU/mL followed by HCV RNA ≥ 50 IU/mL during treatment] or failure to suppress [each measured on-treatment HCV RNA value ≥ 50 IU/mL])
- Relapse (defined as HCV RNA <50 IU/mL at EoT or at the last on-treatment HCV RNA measurement followed by HCV RNA ≥ 50 IU/mL post-treatment and completed treatment as defined previously)
- Death and none of the above
- Premature study drug discontinuation with no on-treatment virologic failure and none of the above
- Insufficient virological response, other than those mentioned above (patients for whom insufficient virological response was reported, or who had HCV RNA ≥ 50 IU/mL post EoT and no HCV RNA test on treatment) and none of the above
- Missing SVR12 data and/or none of the above criteria

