Virological response rates and non-response categories will be displayed for patients who completed treatment with AbbVie regimen, as well.

SVR12 (Exploratory Analyses)

Univariate and multiple logistic regression (MLR) methods will be used to investigate the impact of various explanatory covariates (patient and disease characteristics) at baseline on SVR12.

These analyses will be of exploratory nature, data driven, and will be performed for CP population. Univariate logistic regression will be performed first and then backward selection procedures will be applied to generate the final MLR model. A p-value <0.05 will be used for the covariates to stay in the model in a backward elimination step. If the percentage of patients with available data for a variable is lower than 80% of the patient group analyzed, then this variable will not be considered in the MLR analysis.

The variables to be considered are as follows:

- Key demographic information
 - Age (continuous)
 - Gender (Female [reference], Male)
 - Race/ethnic origin (White/Caucasian [reference], Black, Asian/Oriental, Other [all other races]); at least two categories with at least 10% of the patients each have to exists, so that this variable will be considered
 - Weight (continuous)
 - BMI (continuous)
 - IL28B, rs12979860 (CC [reference], CT or TT); patients with unknown genotype are excluded from the respective analyses.
- CHC disease characteristics
 - Years since diagnosis (continuous)
 - Mode of CHC infection (Drug use [reference], Other [all other answers excluding unknown], unknown);
 - Most recent stage of liver fibrosis (No cirrhosis/Transition to cirrhosis [reference], Cirrhosis; for definition see 4.2.6.2);
- HCV RNA level at baseline (\log_{10} IU/mL)
- HCV genotype(G1a*, G1b, G4; for definition see section 4.2.6.2)
- Type of treating institute (Private Practice / Private Hospital, Academic / University Hospital, General Hospital, Other)
- Co-infections (every patient not reporting the respective co-infection is considered as not having the respective co-infection)
 - HIV(No [reference], Yes)
 - HBV(No [reference], Yes)
- Liver and/or CHC related co-morbidities (every patient not reporting the respective co-morbidity is considered as not having the respective co-morbidity)
 - Liver transplantation (No [reference], Yes)
 - Steatosis (non-alcoholic) (No [reference], Yes)
 - Decompensated liver disease (No [reference], Yes)

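### The SVR12 predictor and adherence regressions are planned only in the core population, where a missing SVR12 counts as failure; no model is re-estimated in CPSFU12, which would reduce the mixing of virological failure with missed follow-up

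*SAP*

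**What the plan says.** SAP section 2 lists as a secondary objective "To provide real world evidence for predictive factors of virological response", and separately the influence of adherence on outcome. SAP 4.2.7.2.1 serves these with univariate and multiple logistic regressions on SVR12: "These analyses will be of exploratory nature, data driven, and will be performed for CP population". The two adherence models use all CP patients and CP patients taking ribavirin. Table 8 lists all three regression outputs for the CP or its ribavirin subset only. The only further SVR12 regressions mentioned are optional models in genotype or cirrhosis subgroups.

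SAP 4.2.3 sets the rule for missing values. Flanking imputation comes first. For SVR, "if there is no value in the appropriate window after flanking imputation but there is an HCV RNA value after the window", that later value is carried back. If nothing is available after that, "the subject will be imputed as a visit failure (i.e., not undetectable or unquantifiable").

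SAP 4.2.1 defines CPSFU12. It drops patients who were responding at their last measurement and have no HCV RNA at 70 days or later "for reasons not related to safety or effectiveness (e.g. lost-to-follow-up or patient not willing to perform an additional HCV RNA test"). It keeps patients whose last value was 50 IU/mL or more, those with reported virological failure but no value, and those without a late value "due to reasons related to safety (e.g. dropped out due to adverse event").

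On its use, SAP 4.2.7.1 says: "In the framework of sensitivity analyses the primary analyses will be repeated for the CPSFU". CPSFU also appears for SVR24, for the response-rate tables including completers (Table 8), and for the interim non-response table (4.2.9). It is not used for any regression.

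**The concern.** The objective concerns virological response, but the modelled outcome is a composite: virological failure or no usable test. With SVR12 planned at 90-95%, failures are few, so a small percentage of missing tests can be a large share of the events. Several candidates in 4.2.7.2.1 (drug use as mode of infection, alcohol use, depression, institution type) plausibly relate to missed visits. That link is an inference; the documents do not state it.

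Two distortions follow. A factor that acts only on attendance can survive backward elimination at p<0.05 and be reported as a predictor of response. A factor with a real virological effect but no link to attendance is pulled towards an odds ratio of 1. Protocol 9.9 recognises that missing HCV RNA lowers the observed SVR rate, but neither document carries this through to the regressions.

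The planned tables would not reveal it. The non-response categories "will be summarized for CP patients, overall and stratified by genotype and cirrhosis status". The disposition tables (4.2.5) add treatment regimen and reasons such as failure to return. Neither breaks missing follow-up down by the other covariates.

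**Working it through.** **The plan's own figure.** Clopper-Pearson limits for n=417 at 90% are 86.71 to 92.71, width 6.00, as in SAP Table 1. Enrolment: 417/0.95 = 439, against 440 stated. The sample size is not in dispute; it only sets the scale: 440 x 0.95 = 418.

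**Assumed inputs, not in the documents.** Virological failure v = 5% among patients with follow-up; a binary factor with no virological effect; missingness m0 without and m1 with the factor; factor prevalence 35%, then 10%. A share k of missing patients stays in CPSFU12 as failures, for example through safety-related loss; the rest are excluded.

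**Formula.** The odds of failure in a group are [v + k·m/(1-m)]/(1-v), so

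OR = [v + k·m1/(1-m1)] / [v + k·m0/(1-m0)].

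The CP is k=1. Example, 4 v 7%: (0.05 + 0.0753)/(0.05 + 0.0417) = 1.37. With k=0 the ratio is v/v = 1.

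**Results.** n=418, prevalence 35%, 200,000 simulated trials per scenario, two-sided Wald test at 0.05. Each cell gives the odds ratio and the share of trials significant.

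| Missing, m0 v m1 | CP | CPSFU12, k=0 | k=0.25 | k=0.5 |
|---|---|---|---|---|
| 4 v 7% | 1.37 (16%) | 1.00 (4%) | 1.14 (6%) | 1.24 (9%) |
| 1 v 4% | 1.53 (19%) | 1.00 (4%) | 1.15 (6%) | 1.29 (9%) |
| 3.75 v 7.5% | 1.47 (22%) | 1.00 (4%) | 1.18 (6%) | 1.30 (11%) |
| 2.5 v 10% | 2.13 (63%) | 1.00 (4%) | 1.38 (12%) | 1.68 (28%) |

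With equal 5% missingness the CP rate is about 4.5%, so the excess comes from the contrast in missingness. At 10% prevalence the CP rates are 11%, 13%, 14% and 36%.

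**Plausibility.** Overall failure at 4 v 7% is 0.65 x 0.088 + 0.35 x 0.1165 = 9.8%, or 41 of 418. Missing tests are 0.65 x 4% + 0.35 x 7% = 5.05%, or 21, which is 52% of failures. At 1 v 4% there are 29 failures, 30% of them missing tests. Across the four scenarios CP SVR12 is 90.1-93.0%, inside the planning range.

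**Dilution.** Take a true odds ratio of 3, 50% prevalence and 5% failure overall; the group risks are 2.60% and 7.40%. With 5% missing in both groups they become 0.05 + 0.95 x 0.0260 = 7.47% and 0.05 + 0.95 x 0.0740 = 12.03%, an odds ratio of 1.70. With 2% missing it is 2.14.

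**Events left in CPSFU12** (all missing patients excluded). At 90% CP SVR12: 41.8 - 8.4 = 33 failures with 2% missing, and 41.8 - 20.9 = 21 with 5% missing. At 95% with 2% missing: 20.9 - 8.4 = 12.5, about 13.

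**Does agreement between the two populations show a virological effect?** Read agreement as the same sign and at least half the CP log odds ratio. At 35% prevalence, a pure missingness factor already significant in the CP passes in about 62%, 59%, 54% and 21% of trials with k=0 (scenarios in table order), and in 56-81% with k=0.25. The populations share every virological failure, so chance imbalance carries over.

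**The case against.** The models are declared exploratory and data driven, and they use the same population and failure rule as the primary analysis, which is coherent for real-world effectiveness. Carry-back of later values limits the number missing, and disposition and completer tables give further description. All of this stands. It lowers the priority but does not answer the point, since none of these outputs shows missing follow-up by drug use, alcohol or depression.

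The size is hypothetical. This also stands: the 63% needs a fourfold contrast in missingness in about a third of patients, all the figures are univariate, and retention in the multiple model was not examined. The planning allowance of 5% not evaluable might itself include missing tests, in which case removing 5% and then assuming about 5% missing would count them twice. The 1 v 4% scenario, with about 2% missing, is less exposed to this.

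A full repeat of the modelling in CPSFU12 would be unstable: about 35 candidate parameters plus an interaction, on about 13-33 failures. This stands and shapes the fix.

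A reader might infer that CPSFU12 isolates virological failure, or that a factor confirmed there is a virological predictor. Neither is supported. By definition CPSFU12 keeps some safety-related losses as failures, and the last check above shows that null factors often pass.

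**Conclusion.** The concern holds as a gap in sensitivity analysis for exploratory models. All three SVR12 regression outputs are CP-only, missing counts as failure, and a population that would reduce the mixing is already defined but not used for them. Under the assumed inputs, a factor acting only on missingness shows a CP odds ratio of about 1.4-2.1, significant in 16-63% of trials at 35% prevalence and 11-36% at 10%. In CPSFU12, at 35% prevalence, this falls to about 4% if every missing patient is excluded, 6-12% if a quarter stay as failures and 9-28% if half stay. These figures illustrate a mechanism; they do not predict this study's results.

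A reader might infer that the primary SVR12 estimate is compromised. It is not: it is reported in the CP and repeated in CPSFU. A reader might also infer that the adherence effect will be overstated by a known amount. The documents do not support a figure. The SAP gives the adherence formula but not how pills are counted after loss to follow-up, and Protocol Table 2 schedules adherence documentation through end of treatment.

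The conclusion rests on the SAP text and Table 8; the table shells in Part II were not available.

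**What to change.** Add to SAP 4.2.7.2.1 and Table 8 a pre-specified sensitivity analysis in CPSFU12:

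- Re-estimate the univariate models, the covariates retained in the final CP model, and the adherence terms. Do not run a new backward selection. Use Firth-penalised estimation where events are sparse.
- Report CP and CPSFU12 odds ratios with confidence intervals side by side, and label the CP version 'SVR12, missing = failure'.
- Under each CPSFU12 model, give the number of failures that are neither on-treatment virological failure nor relapse.
- State that CPSFU12 reduces but does not remove the mixing, and that agreement in direction or rough size is not a rule for calling a factor a virological predictor.

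The cost is SAP wording and matching outputs for the three existing regression tables; no new data are needed. The downside is fewer events (about 13-33 failures under the assumed rates), wider intervals, and possible selection from excluding patients lost to follow-up. For that reason the CP analysis stays and the CPSFU12 version sits beside it.
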